6.3.4.2 Safety

Safety analyses are based on observed values. Any missing safety data including laboratory data will not be imputed. For adverse events (AEs), any events with missing start or stop date will be considered as treatment emergent AEs. For concomitant medications, any medication with missing start or stop dates are considered as Day 1 concomitant medication.

Adverse events with incomplete dates will be categorized as treatment emergent unless there was sufficient specificity to the onset date to document that the event began before the first dose of study medication. No missing dates will be imputed.

6.4. Statistical Analyses

6.4.1. Subject Disposition

Subject disposition will be summarized as follows:

- The number of subjects who signed the informed consent form, are screen failures, are randomized, are treated (Safety Population), completed the study or who discontinued early along with reasons for early discontinuation will be summarized overall and by site for all screened subjects.
- The number of subjects in each analysis population along with reasons for exclusion from each analysis population will be summarized by treatment group for all randomized subjects.
- The number of subjects who complete the study or who discontinued early along with reasons for early discontinuation will be summarized by treatment group for each analysis population.
- The duration on study (number of days from the first date of treatment to the date of last recorded contact/participation date in the database) will be summarized by treatment for each analysis population.
- The number of subjects who are screened, screen failures, and randomized will be summarized by country and site for all screened subjects.
- The number of subjects in each treatment group will be summarized by country and site for each analysis population.

Completers are defined as a subject who completes the Day 540 visit.

A summary of inclusion/exclusion criteria will be provided by treatment group for all screened subjects and for the ITT population.

A summary of the number of subjects by visit will be provided by treatment group for each analysis population.

6.4.2. Protocol Deviations

The number and percentage of subjects with any protocol deviations will be summarized by treatment group. The protocol deviation categories are provided below.

- Subjects with at least one protocol deviation
- Inclusion and/or exclusion criteria violation
- Laboratory assessments not drawn at Day 1, Day 510 or Day 540 (EOS) visits
- Mis-dosing for any reason other than subject safety or withdrawal
- Prohibited concomitant medication / Change in baseline statin or other lipid-lowering therapy dose
- SAE form not reported to MDCO within 24 hours
- Informed consent not signed prior to study entry

6.4.3. Demographic and Background Characteristics

Subject demographics including age, age category (<65 years vs ≥65 years; 18 to <50, 50 to <65, 65 to <75, ≥75 years), race, gender, ethnicity, and country, baseline characteristics such as body height, weight, BMI, waist circumference, current use of statins or other lipid-modifying therapies (yes, no), status of statin intolerance, baseline eGFR, and baseline diabetes status based on HbA1c and fasting glucose will be summarized by treatment group using the ITT, FAS, mITT, and Safety populations.

Medical history (targeted medical history, other medical history, and medical history of statin intolerance) will be summarized by treatment group using the ITT, FAS, mITT and Safety populations.

6.4.4. Study Drug Exposure

Study drug administration will be summarized overall by treatment group and by dosing visits (including, missed doses, and injection site location) for safety population.

6.4.6. Efficacy Analysis

The ITT population will be the primary population for the efficacy analysis. Efficacy analyses will also be performed for the FAS and mITT populations as supportive analyses.

6.4.6.1. Primary Efficacy Endpoints

The co-primary endpoints for this study are:

- Percentage change in LDL-C from baseline to Day 510
- Time adjusted percentage change in LDL-C from baseline after Day 90 and up to Day 540. This is the average percentage change in LDL-C from baseline over the period after Day 90 and up to Day 540.

Note: The time adjusted percentage change in LDL-C from Baseline after Day 90 and up to Day 540 analysis reflects LDL-C effect at a steady state. As such, this analysis assesses the effect on LDL-C levels seen with a more chronic dosing regimen. The Day 90 dose is the start of the 6 monthly dosing regimen.

The statistical hypotheses for the co-primary endpoint of the percentage change in LDL-C from baseline to Day 510 are as follows:

H01: The difference (inclisiran minus placebo), between subjects treated with inclisiran 300mg and placebo in the least squares mean percentage change in LDL-C from baseline at Day 510 = 0.

HA1: The difference (inclisiran minus placebo), between subjects treated with inclisiran 300mg and placebo in the least squares mean percentage change in LDL-C from baseline at Day 510 < 0.

The statistical hypotheses for the co-primary endpoint of the time adjusted percentage change from baseline after Day 90 and up to Day 540 are as follows:

H02: The difference (inclisiran minus placebo), between subjects treated with inclisiran 300mg and placebo in the least squares mean time adjusted percentage change in LDL-C from baseline after Day 90 and up to Day 540 = 0.

HA2: The difference (inclisiran minus placebo), between subjects treated with inclisiran 300mg and placebo in the least squares mean time adjusted percentage change in LDL-C from baseline after Day 90 and up to Day 540 < 0.

The family-wise type I error rate is controlled at a two-sided significance level of $\alpha=0.05$ by using a nested testing procedure. The percentage change in LDL-C from baseline to Day 510 will be tested first. If the null hypothesis is rejected at a two-sided significance level of $\alpha=0.05$ and superiority of inclisiran over placebo is claimed, then the time adjusted percentage change in LDL-C from baseline after Day 90 and up to Day 540 will be tested, also at a two-sided significance level of $\alpha=0.05$.

The primary endpoints will use a reflexive LDL-C approach: either calculated LDL-C (based on the Friedewald formula) will be used, or if the calculated LDL-C is less than 40 mg/dL or triglycerides are greater than 400 mg/dL, or calculated LDL-C is missing, directly measured (using ultracentrifugation) LDL-C will be used if it is available.

Percentage change in LDL-C from baseline to Day 510

Missing values will be imputed for LDL-C after a reflexive approach using the multiple imputation (100 total imputed datasets) washout model specified in [Appendix 2](#). The percentage change in LDL-C at each visit will be calculated after the missing data imputation has been performed.

The primary analysis will be conducted on the ITT population and based on an ANCOVA model on the percentage change in LDL-C from baseline to Day 510 on each multiply imputed dataset (100 total). The model will include fixed effects of treatment group and current use of statins or other lipid-modifying therapies at baseline (yes or no) and baseline LDL-C as a covariate.

Treatment effects from these 100 ANCOVA analyses will then be combined using Rubin's Method via the SAS PROC MIANALYZE procedure. The difference in the least squares means

between treatment groups and corresponding two-sided 95% confidence interval will be provided for hypothesis testing.

See [Appendix 2](#) for more details on this analysis.

Time adjusted percentage change in LDL-C from baseline after Day 90 and up to Day 540.

A control-based pattern-mixture model (PMM), following the methods described in [Ratitch and O’Kelly \(2011\)](#), will be utilized to explore the possibility of data missing not at random (MNAR) for subjects who discontinued the study. For subjects who discontinued the study without any further follow-up data, their missing values after study discontinuation will be imputed under the assumption that their outcome would be similar to those in the placebo group with similar background characteristics. For subjects who did not discontinue the study, their intermittent missing values will be imputed based on the MAR assumption. Multiple imputations will be used to account for uncertainty in the imputation process and results from the imputed datasets will be combined using Rubin’s method [[Rubin, 1987](#)]. See [Appendix 3](#) for more details on this analysis.

The primary analysis will be conducted on the ITT population and based on a mixed-effects model for repeated measurements (MMRM) on the percentage change in LDL-C from baseline over all visits on each multiply imputed dataset (100 total). The model will include fixed effects for treatment, visit, baseline value, interaction between treatment and visit, and current use of statins or other lipid-modifying therapies. The Restricted Maximum Likelihood (REML) estimation approach will be used with the covariance structure set as “Unstructured” (refer to [Appendix 1](#) for further details on the MMRM).

The time adjusted percentage change in LDL-C from baseline after Day 90 and up to Day 540 will be calculated from the MMRM. Linear combinations of the estimated means after Day 90 and up to Day 540 will be used to compare treatment effects.

Treatment effects from these 100 MMRM analyses will then be combined using Rubin’s Method via the SAS PROC MIANALYZE procedure. The difference in the least squares means between treatment groups and corresponding two-sided 95% confidence interval will be provided for hypothesis testing.

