6.2. Randomization

Subjects will be screened and approximately 1500 eligible subjects will be randomized by the IRT system: 750 subjects will be randomized to inclisiran sodium 300 mg and 750 subjects to placebo. Treatment allocation will be stratified by country and by current use of statins or other lipid-modifying therapies. Each subject will receive four SC injections of blinded inclisiran or placebo on Day 1, Day 90, Day 270, and Day 450.

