6.4.6.1.1. Sensitivity Analysis for Primary Efficacy Endpoints

In order to support the robustness of the conclusions drawn from the co-primary efficacy analyses, we will perform the following sensitivity analyses for the co-primary efficacy endpoints.

Percentage change in LDL-C from baseline to Day 510

- A control-based pattern-mixture model (PMM), using the same imputed datasets and MMRM model that was used for the second co-primary efficacy endpoint primary analysis will be used to compare treatments at Day 510. Multiple imputations will be used to account for uncertainty in the imputation process and results from the imputed datasets will be combined using Rubin’s method. (Refer to [Appendix 3](#) for details)
- A mixed model for repeated measurements (MMRM) analysis without multiple imputation, that assumes missing data are missing at random (MAR), will be performed. The model will include fixed effects for treatment, visit, baseline value, interaction

between treatment and visit, and current use of statins or other lipid-modifying therapies. The Restricted Maximum Likelihood (REML) estimation approach will be used with the covariance structure set as “Unstructured”. A linear contrast at Day 510 will be used to compare treatment groups. This will be the same model that is used as a sensitivity analysis for the second co-primary endpoint.

- The impact of country will be assessed by including country (possibly pooled into a region) and the treatment-by-country interaction fixed effects into the primary efficacy analysis ANCOVA (using multiple imputation washout model data).
- A tipping point analysis will be performed to search for the tipping point that reverses the study conclusion. In the tipping point analysis, we will independently vary the deltas in the treatment groups (inclisiran group progressively worse while the placebo group is not impacted and inclisiran group progressively worse while the placebo group progressively improves) until the hypothesis test on the co-primary efficacy endpoint becomes statistically insignificant. The MNAR(ADJUST) statement in SAS PROC MI will be used to adjust the delta of the imputed missing values analyzed using the ANCOVA model with washout model multiply imputed data.

Time adjusted percentage change in LDL-C from baseline after Day 90 and up to Day 540.

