6.4.6.2. Secondary Efficacy Endpoints

The secondary efficacy endpoints will not be tested if either one of the co-primary efficacy endpoints' null hypothesis fails to be rejected.

The key secondary endpoints of this study are:

- Absolute change in LDL-C from baseline to Day 510.
- Time adjusted absolute change in LDL-C from baseline after Day 90 and up to Day 540.
- Percentage change from baseline to Day 510 in PCSK9, total cholesterol, ApoB, and non-HDL-C.

The Hochberg procedure [[Hochberg, 1988](#)] will be applied to control the family-wise type I error rate at a two-sided significance level of $\alpha=0.05$ for the key secondary endpoints.

Missing values will be imputed using the control-based PMM (see [Appendix 2](#) for more details) on LDL-C, PCSK9, total cholesterol, ApoB, and non-HDL-C, absolute change or percent change from baseline will be calculated based on imputed data before any analysis is performed.

The absolute change in LDL-C from baseline to Day 510 and percentage change from baseline to Day 510 in PCSK9, total cholesterol, ApoB, and non-HDL-C will be analyzed using a MMRM with covariates as specified in Appendix 1 and Appendix 3. Time adjusted absolute change in LDL-C from baseline after Day 90 and up to Day 540 will be analyzed similarly to that of time adjusted percentage change in LDL-C from baseline after Day 90 and up to Day 540.

MMRM without multiple imputation (see [Appendix 1](#)) will be used as sensitivity analyses for the key secondary endpoints.

The other secondary endpoints of this study are:

- Maximum percentage change in LDL-C. This is calculated by finding the smallest LDL-C value across all post baseline visits for each individual subject. This value will be used to compare with each subject's baseline value and calculate the percent change from baseline to the lowest LDL-C value.
- Absolute change from baseline to Day 510 in PCSK9, total cholesterol, ApoB and non-HDL-C.
- Absolute change and percentage change in LDL-C from baseline to each assessment time up to Day 540.
- Individual responsiveness defined as the number of subjects reaching on treatment LDL C levels of <25 mg/dL, <50 mg/dL, <70 mg/dL, and <100 mg/dL at Day 510.
- Proportion of subjects in each group with greater or equal to 50% LDL-C reduction from baseline.
- Absolute change and percentage change in other lipids, lipoproteins, apolipoproteins, and PCSK9 from baseline at each subsequent visit to Day 540.

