APPENDIX 1. DETAILS OF MMRM USED FOR EFFICACY ANALYSES

A number of efficacy analyses will utilize a mixed-effects model for repeated measures (MMRM). This includes the co-primary efficacy endpoints (in the case of the first co-primary efficacy endpoint, it will be used as a sensitivity analysis), the key secondary efficacy endpoints, and other secondary efficacy endpoints.

The models will generally include fixed effects for treatment, visit, baseline value, interaction between treatment and visit, and current use of statins or other lipid-modifying therapies. The visits will include Days 90, 150, 270, 330, 450, and 510, with Day 510 as the primary time-point. Linear combinations of the estimated means will be created for the various hypothesis tests.

The Restricted Maximum Likelihood (REML) estimation approach will be used with the covariance structure set as “Unstructured.” The least squares means will be calculated for each treatment at each visit.

The analysis will be carried out using the SAS PROC MIXED procedure.

Sample SAS statements follow:

```
ods output LSmeans=estimates;
ods output Diffs=lsdiffs;
Proc Mixed Data=ldl_data;
  Class treatment visit_day subject_id statiny;
  Model percent_change = treatment|visit_day statiny
base_value/DDFM=KR;
repeated visit_day/type=UN subject=subject_id;
LSMeans treatment*visit_day/cl pdiff=control('0' '510');
run;
```

(where ('0' '510') is the value of the placebo ['0'] at day 510 ['510'] in interaction term treatment*visit_day)

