APPENDIX 2. MULTIPLE IMPUTATION WASHOUT MODEL

A multiple imputation washout model will be utilized for the primary efficacy analysis of the percentage change in LDL-C from baseline to Day 510 endpoint. The washout model can be thought of as a modified control-based Pattern-Mixture Model (PMM) that will be used to explore the possibility of data missing not at random (MNAR) for subjects who discontinued the study early. For subjects who discontinued the study early, their missing values will be imputed under the assumption that their outcome would be similar to those in the placebo group with similar background characteristics. For subjects in the inclisiran group only missing Day 510 values will be imputed. For subjects in the placebo group their missing values over all visits after early termination will be imputed based on the missing at random (MAR) assumption. Multiple imputation will be used to account for uncertainty in the imputation process and results from the imputed datasets will be combined using Rubin's method. Further details are provided below.

Windowing will be performed first (see [Section 6.3.3](#)) and any missing data will be imputed using the following steps.

The covariates and baseline characteristics which can be predictive of the response for the inclisiran group will be included in a multiple imputation procedure (SAS PROC MI) and will include the following:

- Baseline value of efficacy measurement (continuous)
- Observed value of efficacy measurement at Day 510 from the placebo group (continuous)
- Current use of statins or other lipid-modifying therapies (categorical)

The covariates and baseline characteristics which can be predictive of the response for the placebo group will be included in a multiple imputation procedure (SAS PROC MI) and will include the following:

- Baseline value of efficacy measurement (continuous)
 - Observed value of efficacy measurement at Day 90 (continuous)
 - Observed value of efficacy measurement at Day 150 (continuous)
 - Observed value of efficacy measurement at Day 270 (continuous)
 - Observed value of efficacy measurement at Day 330 (continuous)
 - Observed value of efficacy measurement at Day 450 (continuous)
 - Observed value of efficacy measurement at Day 510 (continuous)
 - Observed value of efficacy measurement at Day 540 (continuous)
 - Current use of statins or other lipid-modifying therapies (categorical)

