APPENDIX 3. CONTROL-BASED PATTERN MIXTURE MODEL

A control-based Pattern-Mixture Model (PMM) will be used to explore the possibility of data missing not at random (MNAR) for subjects who discontinued the study. For subjects who discontinued the study without any further follow-up data, their missing values after study discontinuation will be imputed under the assumption that their outcome would be similar to those in the placebo group with similar background characteristics. For subjects who did not discontinue the study, their intermittent missing values will be imputed based on the MAR assumption. Multiple imputation will be used to account for uncertainty in the imputation process and results from the imputed datasets will be combined using Rubin's method. Further details are provided below.

Windowing will be performed first (see [Section 6.3.3](#)) and any missing data will be imputed using the following steps.

The covariates and baseline characteristics which can be predictive of the response will be included in a multiple imputation procedure (SAS PROC MI) and will include the following:

- Baseline value of efficacy measurement (continuous)
 - Observed value of efficacy measurement at Day 90 (continuous)
 - Observed value of efficacy measurement at Day 150 (continuous)
 - Observed value of efficacy measurement at Day 270 (continuous)
 - Observed value of efficacy measurement at Day 330 (continuous)
 - Observed value of efficacy measurement at Day 450 (continuous)
 - Observed value of efficacy measurement at Day 510 (continuous)
 - Observed value of efficacy measurement at Day 540 (continuous)
 - Current use of statins or other lipid-modifying therapies (categorical)
1. Intermittent missing data will be imputed using MCMC methods, assuming MAR, within each treatment group. SAS PROC MI will be utilized for this step using the MCMC impute=monotone option. A total of 100 datasets will be created. These datasets will be utilized in Step #2.

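### Randomisation is stratified by country, but the co-primary models and both imputation models omit it; if country is prognostic, intervals are slightly too wide and tests conservative

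*SAP*

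**What the plan says.** On allocation, SAP 6.2 states: "Treatment allocation will be stratified by country and by current use of statins or other lipid-modifying therapies". Protocol 10.2 agrees.

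The analysis models carry only the second of these factors:

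- **First co-primary, ANCOVA (SAP 6.4.6.1; Appendix 2, step 6).** "The model will include fixed effects of treatment group and current use of statins or other lipid-modifying therapies at baseline (yes or no"), plus baseline LDL-C as a covariate.
- **Second co-primary, MMRM (SAP 6.4.6.1).** "The model will include fixed effects for treatment, visit, baseline value, interaction between treatment and visit", together with the lipid-therapy factor. The code in Appendix 1 matches: its class statement is "Class treatment visit_day subject_id statiny", and country is not in the model statement.
- **Key secondaries (SAP 6.4.6.2).** The Day 510 endpoints "will be analyzed using a MMRM with covariates as specified in Appendix 1 and Appendix 3", so they inherit the omission. The time-adjusted absolute change is handled like the second co-primary.
- **Imputation.** Appendix 2 lists baseline, visit values and "Current use of statins or other lipid-modifying therapies (categorical"). Appendix 3 says "The covariates and baseline characteristics which can be predictive of the response will be included in a multiple imputation procedure (SAS PROC MI") and gives the same kind of list. Neither includes country.

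Country appears only in SAP 6.4.6.1.1. For the first co-primary, country (which may be pooled into regions) is added with "treatment-by-country interaction fixed effects into the primary efficacy analysis ANCOVA (using multiple imputation washout model data"). A parallel model is planned for the second co-primary, on its own imputed data.

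Protocol 10.4.3.1 also leaves country out of the model, so the two documents do not conflict. Neither gives a reason for treating the two stratification factors differently.

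**The concern.** Balancing the arms within country removes between-country differences from the treatment comparison. The estimate gains that precision whatever model is fitted. The model-based standard error reflects the gain only if country is in the model; otherwise between-country variation stays in the residual. The two-sided 95% intervals that SAP 6.4.6.1 uses for hypothesis testing are then wider than they should be, and the p-values larger.

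The documents give some reason to think country could matter, though not how much. Protocol Appendix B allows lower statin doses where the locally approved maximum is lower, so background intensity can differ by country. A yes/no therapy term cannot capture that, although baseline LDL-C may capture part of it. The SAP itself plans to examine the effect of country.

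What is at stake is whether intervals and p-values match the randomisation. The primary conclusion is not at stake.

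**Working it through.** **Where each stratification factor is used**

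| Component | Lipid therapy | Country |
|---|---|---|
| Randomisation (Protocol 10.2; SAP 6.2) | yes | yes |
| ANCOVA, first co-primary | yes | no |
| MMRM, second co-primary | yes | no |
| MMRM, key secondaries | yes | no |
| Washout imputation (Appendix 2, both arms' lists) | yes | no |
| Control-based imputation (Appendix 3) | yes | no |
| Country sensitivity models, co-primaries only | yes | main effect plus interaction |

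**The plan's own figures (SAP 6.1).** Inputs: 1,500 randomised, 5% dropout, difference 30 mg/dL, SD 20 mg/dL, one-sided alpha 0.025.

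- Evaluable: 1,500 × 0.95 = 1,425, or 712.5 per arm.
- SE = 20 × √(2/712.5) = 1.060 mg/dL.
- z = 30/1.060 = 28.3, so power is about 1.000. The stated power of more than 90% holds.

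**Effect of omitting country.** Let R² be the share of residual variance due to country after baseline LDL-C and lipid therapy. The documents do not give it. I assume 0% to 10%, with 20% as an extreme. With balance within country and complete data:

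- reported SE / true SE = 1/√(1 − R²)
- actual one-sided alpha = P(Z > 1.96/√(1 − R²))
- true coverage = 1 − 2 × that alpha
- correct planning SE = 1.060 × √(1 − R²), treating the planning SD as the residual SD including country

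| Assumed R² | SE ratio | One-sided alpha | Coverage of 95% CI | Correct SE (reported 1.060) | Correct CI half-width (reported 2.077) |
|---|---|---|---|---|---|
| 0% | 1.000 | 0.0250 | 95.0% | 1.060 | 2.077 |
| 2% | 1.010 | 0.0239 | 95.2% | 1.049 | 2.056 |
| 5% | 1.026 | 0.0222 | 95.6% | 1.033 | 2.024 |
| 10% | 1.054 | 0.0194 | 96.1% | 1.005 | 1.970 |
| 20% | 1.118 | 0.0142 | 97.2% | 0.948 | 1.858 |

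**Simulation under the null: two-sided rejection at 0.05.** The documents give neither the number of countries nor the block size, so two assumed layouts were used, each with n = 1,500. Layout A has 10 equal countries with exact balance (20,000 runs, Monte Carlo error 0.0015). Layout B has 8 unequal countries with permuted blocks of 4 within country by lipid-therapy stratum (4,000 runs, Monte Carlo error √(0.05 × 0.95/4,000) = 0.003).

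| R² | A, no country | A, with country | B, no country | B, with country |
|---|---|---|---|---|
| 0% | 0.051 | 0.051 | 0.053 | 0.053 |
| 2% | 0.047 | 0.050 | 0.047 | 0.048 |
| 5% | 0.045 | 0.050 | 0.044 | 0.050 |
| 10% | 0.039 | 0.051 | 0.034 | 0.044 |
| 20% | not run | not run | 0.027 | 0.050 |

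In layout A at R² = 10% (outcome in units of its SD), the true SD of the estimate was 0.0487 in both models. The mean reported SE was 0.0516 without country and 0.0490 with it. In layout B at the same R², on the 20 mg/dL scale, the empirical SD was 0.965 in both models, against a mean reported SE of 1.033 without country and 0.980 with it. So the estimate is equally precise either way, and only the reported SE is wrong.

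**The case against.** The best case for leaving the model alone has five parts.

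- **No decision changes.** The omission is conservative, z is about 28, and the SE excess is about 0.05 mg/dL even at R² = 10%. This stands, and it is why the point is minor.
- **The size rests on an assumption.** R² is not in the documents and could be zero. This also stands. The direction is certain only if country is prognostic.
- **The mg/dL figures are not on the co-primary scale.** The co-primaries are percentage changes, and SD 20 is a planning SD. That is correct. The SE ratios, alpha and coverage do not depend on the scale. Power for a 30-point difference stays at 0.9999 even with an SD of 100.
- **The planned sensitivity models already contain country.** This is partly right. With 10 equal, exactly balanced countries (3,000 runs per R²), the equally weighted treatment effect from the interaction model matched the main-effect estimate (correlation above 0.9999), with the same mean SE: 0.0511, 0.0503 and 0.0490 at R² of 2%, 5% and 10%. With very unequal countries and equal weighting it did not: in one assumed layout the mean SE was 0.077 against 0.050. The SAP gives neither the country weights nor a pooling rule, uses data imputed without country, and plans no such model for the key secondaries.
- **The model is prespecified and has regulatory history.** SAP section 8 says the primary analyses and imputation were changed after FDA feedback. It does not mention country, so it neither supports nor excludes the omission.

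**Conclusion.** The concern holds, as a minor one. A factor used to stratify allocation is left, without explanation, out of every primary and key secondary model and both imputation models. If country explains 2% to 10% of residual variance, standard errors are overstated by 1.0% to 5.4% and 95% intervals cover 95.2% to 96.1%. If it explains none, nothing changes. Type I error is not inflated, no information is lost and the co-primary decisions are safe.

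These figures assume complete data and good balance within country. The imputation omission is a separate, smaller matter of consistency between imputation and analysis models. It was not quantified. It concerns about 1,500 × 0.05 = 75 subjects at the planned dropout, and if dropout differs by country the direction of any shift cannot be determined from the documents.

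**What to change.** 1. Add country, as recorded in the IRT at randomisation, as a fixed main effect in the ANCOVA and in the MMRM for the second co-primary and the key secondaries.
2. Add country as a covariate in the Appendix 2 and Appendix 3 imputation models.
3. Fix a rule for pooling small countries before unblinding. The existing country sensitivity analyses need one anyway. It matters most in the imputation steps fitted within a single arm. Coarser pooling recovers less of the correction.
4. Keep the treatment-by-country models as sensitivity analyses, and state how countries are weighted in the overall treatment contrast.
5. Record the change from Protocol 10.4.3.1 in SAP section 8.

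If the primary model is to stay as it is, state why country is omitted and add a sensitivity analysis with country as a main effect only, for each co-primary and preferably for the key secondaries.

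The cost is SAP text, one term per model and a few degrees of freedom out of about 1,500. No new data are needed, because country is already recorded for randomisation.
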